4 GENERAL STATISTICAL CONSIDERATION

4.1 Analysis Sets

The primary and pre-specified additional endpoints will be analyzed on a per-protocol basis. Only enrolled subjects who receive the first treatment will be included in the analysis sample.

4.2 Control of Systematic Error/Bias

Selection of subjects will be made from the Investigators' general or professional referral population. All subjects meeting the inclusion/exclusion criteria and that have signed the protocol-specific ICF will be eligible for enrollment in the trial. Consecutively eligible subjects should be enrolled into the trial to minimize selection bias. In determining subject eligibility for the trial, the investigator's assessment of imaging will be used. However, the MRI core laboratory will independently analyze the images and the data obtained from the core laboratory will be utilized for analyses.

4.3 Enrollment for Each Investigative Site

Each site will be allowed to enroll up to 25% of the total enrollment, with a maximum enrollment of 27 subjects.

4.4 Baseline Data Analyses

Baseline demographics, procedure and assessments will be summarized for the study. For continuous and/or ordinal variables, the descriptive statistics will include mean, standard deviation, number evaluated, minimum and maximum. Some specific variables may also include additional statistics such as median and confidence intervals. For binary or categorical variables,

the descriptive statistics will include percentage, numerator, denominator, and number evaluated. Some variables may include confidence intervals as needed.

The following assessments will be performed during the follow up visits as well as the baseline visit and change from baseline analysis may be performed on clinically meaningful variables.

- Physical examination
- Child-Pugh score
- ECG
- Laboratory tests
- Imaging and tumor measurement
- ECOG performance status
- Concomitant medication

5 ADDITIONAL STATISTICAL ANALYSES

5.1 Secondary Endpoints Assessments

The study is not powered for the secondary endpoints therefore there are no formal hypotheses. The secondary endpoints and analyses are shown below.

- ORR at 30 days and 3-month
- Time to progression (TTP)
- Time to extrahepatic spread (EHS)
- Proportion progression-free (PPF) at one year
- Overall survival (OS) at one year
- The frequency of treatment associated adverse events

Kaplan-Meier analyses will be used for time-to-event type of endpoints such as overall survival (OS), time to progression (TTP), and time to extrahepatic spread (EHS) through 12 months. A binary proportion will be presented for ORR at 30-day and 3-month and progression-free (PPF) rate at 12 months. A frequency will be provided for treatment associated adverse events.

All additional assessments are observational.

5.2 Interim Analyses

No formal interim analyses are planned for the purpose of stopping this study early declaring for efficacy or futility.

5.3 Subgroup Analyses

Primary endpoints and/or additional assessments will be summarized by the following categories (but not limit to):

- Gender (male vs. female)
- ECOG Score (0 vs. 1)
- BCLC Stage (A vs. B7)

All subgroup analyses are observational. No formal tests of hypotheses are proposed for subgroups and therefore alpha-adjustment for multiple comparisons will not be used.

5.4 Missing Data, Drop-Outs, and Protocol Deviations Handling

Boston Scientific will employ robust oversight in order to minimize the loss of subjects throughout any trial follow-up. Additionally, the case report forms are easy-to-follow and maximize the data collection required at each follow-up visit without placing undue burden on the subject. Strategies that are planned to be utilized in the study include:

- Ensure that site personnel are properly trained on the data that is required to be collected and the importance of planning for the follow-up visits.
- Tools in the site's Manual of Operations to assist with follow-up visit planning (e.g. follow-up wheels or similar tools).
- The use of trial newsletters to remind sites of upcoming visits and other project-related milestones to ensure data is being entered promptly and is complete.

5.5 Sensitivity Analysis for Missing Outcome Data

Sensitivity analyses for the primary effectiveness endpoint assessment will be conducted to assess the impact of missing data on the result's robustness. In addition to the use of the worst-case analysis, the tipping point analysis will be performed as post-hoc analysis to consider all combinations of present/absent for all subjects with missing primary outcome.

5.6 Multivariable Analyses

Univariate and multivariable analyses may be performed as post-hoc analyses to assess the effect of potential predictors for the primary effectiveness endpoint in a logistic regression model.

As requested, clinically and/or statistical meaningful baseline covariates will be selected in the regression model. For the 6-month ORR, the predictors will be listed in ascending order of p-value. Univariate analyses will be performed overall as well as separately for each treatment group. For the multivariable analyses, only coefficients in the final model, i.e., with p-values less than 0.1 will be listed.

No formal conclusion will be made by this secondary post-hoc analysis.

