12.3.4. Multivariable Analyses

Univariate and multivariable analyses may be performed as post-hoc analyses to assess the effect of potential predictors for the primary endpoint in a logistic regression model.

Form/Template 90702637 Rev/Ver AH STOPPER China Protocol, 92040370 Rev/Ver AD Page 31 of 59

Clinically and/or statistical meaningful baseline covariates will be selected in the regression model if the analysis is performed.

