1 PROTOCOL SYNOPSIS

1 480 5 61			
A Single-arm Trial of Transcatheter Arterial Chemoembolization with Tandem Microspheres in the Treatment of Localized Hepatocellular Carcinoma			
Study Objective	The primary objective of this study is to evaluate the safety and efficacy of transcatheter arterial chemoembolization with Tandem Microspheres loaded with Epirubicin in the treatment of subjects with localized hepatocellular carcinoma (HCC)		
Study Device	Tandem Microspheres are spherical, tightly calibrated, biocompatible, non-resorbable, hydrogel microspheres coated with Polyzene®-F, an inorganic polymer.		
Planned Indication(s)	Tandem Microspheres are indicated	d for the	
for Use	embolization of arteriovenous malf	formations and	
	hypervascular tumors		
Device Specifications	Tandem Microspheres are stored in 2 ml and 3 ml sized syringes. They are available in a range of sizes (40, 75, and 100 µm). Microspheres used will be at the discretion of the treating physician(s) based on the tumor size and/or vascular structure.		
	Microspheres Diameter (μ])	Size (ml)	
	40	2	
	40	3	
	75	2	
	75	3	
	100	2	
	100	3	
Study Design	This is a prospective, single-arm, multicenter study to evaluate the safety and efficacy of transcatheter arterial chemoembolization with Tandem Microspheres loaded with Epirubicin in the treatment of subjects with localized hepatocellular carcinoma. All qualified subjects will be enrolled in the study and receive transcatheter arterial chemoembolization treatment with Tandem Microspheres loaded with Epirubicin		
Sample Size	109 subjects (including 10% loss to follow-up)		
Number of Study Sites	10 clinical centers will be participating in the study		
Primary Effectiveness Endpoint	The primary effectiveness endpoint for this clinical trial is 6-month objective tumor response rate (ORR).		

Secondary Endpoints	ORR at 30-day and 3-month
	• Time to Progression (TTP)
	Time to Extrahepatic Spread
	Proportion Progression-Free (PPF) at one year
	Overall survival at one year
	The frequency of Tandem treatment associated adverse
	events

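### If the optional predictor analysis in SAP 5.6 is run, listing only multivariable coefficients with p<0.1 will tend to exaggerate modest effects and can print chance ones

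*SAP*

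**What the plan says.** SAP 5.6 makes the analysis optional and post hoc: "Univariate and multivariable analyses may be performed as post-hoc analyses to assess the effect of potential predictors for the primary effectiveness endpoint". The candidates are neither named nor counted: "As requested, clinically and/or statistical meaningful baseline covariates will be selected in the regression model". Two listing rules follow. The first ranks without a cut-off: "For the 6-month ORR, the predictors will be listed in ascending order of p-value". The second filters: "For the multivariable analyses, only coefficients in the final model, i.e., with p-values less than 0.1 will be listed". The section also asks for a by-group run, "Univariate analyses will be performed overall as well as separately for each treatment group", although the SAP synopsis states "This is a prospective, single-arm, multicenter study". It closes with a disclaimer: "No formal conclusion will be made by this secondary post-hoc analysis".

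Protocol 12.3.4 is likewise optional: "Univariate and multivariable analyses may be performed as post-hoc analyses to assess the effect of potential predictors for the primary endpoint". It lets covariates be chosen on clinical or statistical grounds, but has no p<0.1 listing rule and no by-group instruction. Both were added in the SAP.

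**The concern.** A table that prints only coefficients below a significance cut-off reports estimates chosen for being large relative to their standard error. In a small data set a modest true effect reaches p<0.1 mainly when chance has pushed its estimate away from 1, so the printed odds ratio overstates it. Covariates with no effect also pass about one time in ten each. From the multivariable table alone, a reader cannot see how many candidates were tried or what adjusted estimates the others had.

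What is at stake is how an exploratory table is read. SAP 2 allows the specified analyses to go to regulators, scientific meetings and journals, and a reader there may take the printed adjusted odds ratios at face value.

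**Working it through.** **Inputs from the documents** (Protocol 12.1.1.2, SAP 3.1.3): performance goal 45%, expected ORR 60%, one-sided alpha 2.5%, power 85%, 98 evaluable, 10% attrition, 109 enrolled.

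**Reproducing the plan's own figure.** n = [(1.960·√(0.45·0.55) + 1.036·√(0.60·0.40)) / 0.15]² = 97.7, rounded up to 98. Power at 98 is 85.1%. 98/0.90 = 108.9, rounded up to 109. The sample size reproduces. At 60% ORR there are about 98 × 0.40 = 39 non-responders to support the regression.

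**Assumptions, because SAP 5.6 gives none of these:** number of candidates (3 to 20), independent binary covariates, prevalence 50% (20% as a variant), and backward elimination at p<0.1 as the route to the final model.

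**Step 1: how large an odds ratio must be to be listed.** For a single binary covariate, the standard error of the log odds ratio is roughly 1/√(n·p(1−p)·q(1−q)), with p the ORR and q the prevalence.
- 50% prevalence: 1/√(98·0.24·0.25) = 1/√5.88 = 0.412. Two-sided p<0.1 needs |log OR| > 1.645·0.412 = 0.678, that is, an OR above about 1.97 or below about 0.51.
- 20% prevalence: 1/√(98·0.24·0.16) = 1/√3.76 = 0.515. The threshold is 0.848, an OR above about 2.3.

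So in this setting a true OR of 1.5 can be listed only when it is overestimated.

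**Step 2: simulated inflation, n = 98, ORR 60%.**

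Eight candidates, one of them a true predictor, 50% prevalence:
- True OR 1.5: listed in 27% of trials, at a median OR of about 2.5 (2.5 to 2.6 over repeated runs). The unfiltered full model gives a median of 1.6.
- True OR 2.0: listed in 50% of trials, at a median of about 2.8. The unfiltered full model gives 2.1.

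A single predictor, 4,000 runs per scenario, geometric means:
- 50% prevalence, all estimates reported: 1.53 for a true 1.5 and 2.02 for a true 2.0. Only p<0.1 reported: 2.54 and 2.85.
- 20% prevalence, only p<0.1 reported: 3.4 and 4.1.
- True OR 1.0, 50% prevalence: when listed, the effect averages 2.4-fold in one direction or the other.

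The unfiltered estimates lie close to the truth, so most of the exaggeration comes from the filter.

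**Step 3: chance listings when no candidate matters.** P(at least one) = 1 − 0.9^k.
- k = 3: 27% (simulated backward elimination 27%)
- k = 4: 1 − 0.656 = 34%, about 35%
- k = 5: 41% (simulated 40%)
- k = 8: 57% (simulated 58%)
- k = 10: 65% (simulated 66%)
- k = 20: 88%

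The expected number of false listings is 0.1·k: 0.3 at k = 3, 1.0 at k = 10 and 2.0 at k = 20.

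**The case against.** The best defence is that this table is optional, is labelled post hoc, and may support no formal conclusion. It touches neither the primary test nor alpha, power or sample size. All of that stands and limits the point to a minor one. The disclaimer governs what may be concluded, however. It does not correct odds ratios that have already been selected for size.

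The second defence is that the magnitudes rest on inputs the SAP does not state: the number of candidates, their prevalence and the selection method. That also stands. The direction of the bias does not depend on those choices, but its size does, and a strong true predictor would be inflated little.

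Several stronger readings are tempting, and the documents do not support them:
- A reader might infer that the table is bound to mislead. The analysis may never be run, and with no true predictor roughly 35% to 65% of trials would list nothing for 10 down to 4 candidates.
- A reader might infer that covariates failing p<0.1 vanish from the report. The cut-off applies to the multivariable table only. On the natural reading, the list ranked by p-value covers the univariate results, and it has no cut-off. What is shown selectively is the adjusted estimates.
- A reader might infer that this is the only look at ORR by baseline factor. SAP 5.3 and Protocol 12.3.2 also summarise the primary endpoint by gender, ECOG score and BCLC stage, with no p-value filter.
- A reader might infer that the by-group instruction is an analysis that cannot be performed. With one group it simply returns the overall result, so nothing is lost.
- A reader might read the small number of non-responders as calling for a fixed cap on candidates. Any such cap rests on a rule of thumb found in neither document, and is a preference.

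**Conclusion.** The point holds as a minor reporting defect, conditional on the analysis being run. At the planned size, and under the assumptions listed in the working, the p<0.1 rule turns modest true odds ratios of 1.5 and 2.0 into listed medians of about 2.5 and 2.8 with 8 candidates. It produces at least one chance listing in about 35% (4 candidates) to 65% (10 candidates) of trials in which nothing predicts response. These figures show the scale of the problem; they do not forecast this trial's table. The trial's primary conclusion is untouched. The by-group wording is an editorial leftover with no effect on results.

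**What to change.** In SAP 5.6, replace the p<0.1 listing sentence with: *All candidate baseline covariates examined are listed with odds ratio and 95% CI, from the univariate models and from the multivariable model containing all candidates, whatever their p-values.* A reduced model may be shown in addition if it is labelled as selected.

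As an editorial clean-up only, delete the clause asking for univariate analyses by treatment group.

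SAP 5.12 provides for an amended SAP approved before the primary endpoint analysis, so this is a wording change with no effect on data collection. The downside is a few more table rows and more non-significant predictors on show.

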5.7 Time-To-Event Kaplan-Meier Analysis

The Kaplan-Meier product-limit method will be used to estimate event or event-free rates for time-to-event outcomes as post-hoc analyses, such as OS, TTP, EHS, and PPF through 12 months.

5.7.1 Kaplan-Meier for OS

OS is defined as the length of time from the treatment initiation, that treated subjects are still alive. The Kaplan-Meier analysis is aimed to capture the all-cause death for each subject. Subjects who are lost-to-follow will be considered being censored.

There are three critical data items to be captured:

- Death date
- The very last date in the database (e.g. follow-up visit date and/or site reported AE date)
- The desired cut-off days (e.g. 6-month OS at 182 days, 12-month OS at 365 days)

In addition to the Kaplan-Meier survival curve, the median survival time (mOS) will also be used to represent the study cohort.

5.7.2 Kaplan-Meier for TTP

TTP is defined as the length of time from the treatment initiation to either the date of the first disease progression occurred, as assessed by the investigators, or the date of the subject died due to any cause, whichever comes earlier.

TTP (also referred as "time to treatment failure") will be measured by a few data items list below:

- The date of the disease progression in the Overall Response form
- The date of lost-to-follow due to:
 - o Adverse events
 - o Progressive disease/insufficient therapeutic response
 - Death
 - o Failure to return
 - o Refusing treatment/being unwilling to cooperate/withdrawing consent
- The very last date by scanning all available dates in the database
- The desired cut-off days

In addition to the Kaplan-Meier estimates, the median will also be used to represent the study cohort.

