5.2. Device Labeling

STOPPER China Manuel of Operations includes Instruction for Use for Tandem

Form/Template 90702637 Rev/Ver AH STOPPER China Protocol, 92040370 Rev/Ver AD Page 18 of 59

Microspheres. The labeling includes the following information:

- Product Name
- UPN
- Lot Number
- Specification (Diameters of microspheres in µm) and dosage (ml)
- Expiration Date

The labeling of products used for STOPPER China clinical trial should include the following statement:

Used for clinical trial only

The device labeling in Chinese weill be provided per China's regulatory requirement.

6. Study Objective

The primary objective of the study is to evaluate the safety and efficacy of transcatheter arterial chemoembolization with Tandem Microspheres loaded with Epirubicin in the treatment of subjects with localized hepatocellular carcinoma (HCC).

[figure not shown]
7. Study Endpoints

The primary efficacy endpoint is overall ORR at 6 months. The secondary endpoints are:

- ORR at 30 days and 3-month
- Time to Progression (TTP)
- Time to Extrahepatic Spread
- Proportion Progression-Free (PPF) at one year
- Overall survival at one year
- The frequency of treatment associated adverse events

8. Study Design

This is a prospective, single-arm, multicenter study. The flow chart of the study is as follows:

Form/Template 90702637 Rev/Ver AH STOPPER China Protocol, 92040370 Rev/Ver AD Page 20 of 59

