27. Abbreviations and Definitions

See Table 27.1 for Abbreviations.

Table 27.1 Terms and Abbreviations

Table 27.1 Terms and Abbreviations		
AE	Adverse Event	
ALT	Alanine aminotransferase, Serum glutamic pyruvic transaminase (SGPT)	
AST	Asparagine aminotransferase, Serum glutamic oxaloacetic transaminase	
	(SGOT)	
AVM	Arteriovenous malformation	
BCLC	Barcelona Clinical Liver Cancer staging	
CBC	Complete Blood Count	
CR	Complete Response	
CRO	Contract Research Organization	
cTACE	Conventional transarterial chemoembolization	
CRF	Case Report Form	
DEB-TACE	Drug eluting bead-transarterial chemoembolization	
DSMB	Data Safety Monitoring Board	
EC	Ethics Committee	
ECG	Electrocardiogram	
ECOG	Eastern Cooperative Oncology Group	
eCRF	Electronic Case Report Form	
EDC	Electronic Data Capture	
GCP	Good Clinical Practices	
HBV	Hepatitis B virus	
HCC	Hepatocellular Carcinoma	
HCV	Hepatitis C virus	
ICH-GCP	International Conference on Harmonization-Good Clinical Practices	
IDE	Investigational Device Exemption	
INR	International normalized ratio	
IRB	Institutional Review Board	
IRRP	Independent Response Review Panel	
ISO	International Standards	
ITT	Intent-to-Treat	
mRECIST	Modified RECIST	
MRI	Magnetic Resonance Imaging	
PD	Progressive Disease	
PR	Partial Response	
SAE	Serious Adverse Event	
SD	Stable Disease	
TACE	Transarterial chemoembolization	
TTP	Time to Disease Progression	
UADE	Unanticipated Adverse Device Effect	

[figure not shown]
See Tables 27.2 for Definitions

Table 27.2: Definitions

Term	Definition
BCLC Staging System	The Barcelona Clinic Liver Cancer Staging System is a well-accepted system that uses tumor stage, liver function, physical status, and cancer related symptoms, to classify the stages with a treatment algorithm. ⁴
Child-Pugh Score	The Child-Pugh score is a measure of liver function. ⁴ It is calculated from the sum of the points for each Child Pugh Classification (CPC) criteria. See Appendix B
ECOG Performance Status	An Eastern Cooperative Oncology Group (ECOG) assessment of performance status describes a patient's level of functioning in terms of their ability to care for them self, daily activity, and physical ability (walking, working, etc.). See Appendix A.
Investigational Device	Boston Scientific Corporation ONCOZENE™ or TANDEM™ Microspheres loaded with doxorubicin
mRECIST Criteria	A post-treatment assessment of tumor response by magnetic resonance imaging (MRI) scan. See Appendix C.

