5.7.3 Kaplan-Meier for EHS

The time to EHS is defined as the length of time from the treatment initiation to the development of extrahepatic spread of the disease via imaging assessment.

The data items to be considered will include:

- The date of the extrahepatic spread in the Overall Response form
- The very last date by scanning all available dates in the database
- The desired cut-off days

5.7.4 Kaplan-Meier for PPF

PPF is defined as the length of time from the treatment initiation, that treated subjects are still progression-free.

The data items to be captured will include:

- The date of the disease progression in the Overall Response form
- The very last date by scanning all available dates in the database
- The desired cut-off days

The proportion of any time point will be determined by the Kaplan-Meier estimates.

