7.1 Derivation of Variables

- The number of subjects included in the event rates (overall and individual components) will be based on subjects who have adequate follow-up and/or have experienced any component of events within the analysis interval.
- The last follow-up date will be the latest of the following dates for each subject: onset date of an event, DEB-TACE dates, treatment evaluation follow-up dates, end of study date, end of treatment date, and follow-up visit dates.
- Days to event (or last known status) = event (or status) date index procedure date (e.g. DEB TACE1).

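### SAP 5.7.2 labels a progression-or-death composite as TTP and dates it on investigator reads; PPF has two estimators, and its handling of deaths and censoring is not stated

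*SAP*

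**What the plan says.** **TTP.** Protocol section 7 lists time to progression as a secondary endpoint, and Table 27.1 expands TTP as "Time to Disease Progression". Neither mentions death. SAP 5.7.2 ends TTP at "first disease progression occurred, as assessed by the investigators, or the date of the subject died due to any cause, whichever comes earlier" and gives time to treatment failure as another name for it.

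**Whose read.** SAP 4.2 says that "the MRI core laboratory will independently analyze the images and the data obtained from the core laboratory will be utilized for analyses", and Protocol 12.2.2 says the same. SAP 4.2 reserves the investigator's read for eligibility. Protocol 13.3 has the core laboratory assess EASL and mRECIST response on MRI at baseline, 30 days and 3, 6 and 12 months.

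**PPF.** SAP 5.7.4 states that "PPF is defined as the length of time from the treatment initiation, that treated subjects are still progression-free" and takes the proportion from Kaplan-Meier estimates. Its data items are a progression date, the last date in the database and the cut-off days. Protocol 12.1.2 and SAP 5.1 plan a binary proportion at 12 months. SAP 5.7 calls the Kaplan-Meier analyses post-hoc, although SAP 5.1 plans them for OS, TTP and EHS.

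**Last date.** SAP 5.7.2 to 5.7.4 each list the last date found by scanning every date in the database. SAP 7.1 says "The last follow-up date will be the latest of the following dates for each subject" and then names event onset, treatment, evaluation, visit, end-of-treatment and end-of-study dates. For OS, SAP 5.7.1 adds: "Subjects who are lost-to-follow will be considered being censored". SAP 5.7.2 has an item headed "The date of lost-to-follow due to", followed by reasons that include adverse events, insufficient response and death. It does not say whether these dates are events or censoring dates.

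**The concern.** A reader of the report would take TTP as progression alone and might take PPF as alive and progression-free. As written, TTP also counts deaths, and what PPF does with deaths cannot be told from the text. In an open single-arm trial the independent read is the main protection for imaging endpoints. TTP would rest on the investigators' read while the ORR beside it came from the core laboratory.

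The progression criterion is also open, and the two candidates differ. EASL progression is a 25% increase with no stated reference scan, or new lesions. The mRECIST target-lesion table uses a 20% increase from the smallest sum and has no new-lesion clause.

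Two programmers could follow this SAP and obtain different PPF values from the same data. SAP section 2 allows these results to go to authorities and into manuscripts.

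**Working it through.** **1. The plan's own figure.** No target is given for TTP or PPF. The only sample-size figure is for ORR:

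n = [(1.960·√(0.45·0.55) + 1.036·√(0.60·0.40))/0.15]² = 97.7, so 98; and 98/0.90 = 108.9, so 109.

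Both reproduce, and neither uses TTP or PPF.

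**2. Inputs assumed.** The documents give no progression rate and no death rate for this trial. SAP 5.10.2 quotes one-year survival of 100% for Child-Pugh A and 81% for B, for chronic liver disease in general. I assume that by 12 months p = 25%, 35% or 45% progress and d = 0%, 1%, 3%, 8% or 12% die first, with constant hazards.

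**3. Handling of deaths in PPF.** Let H = −ln(1−p−d) and hp = H·p/(p+d).
- Kaplan-Meier with deaths censored: exp(−hp).
- Alive and progression-free, which is what the 5.7.2 composite estimates: 1−p−d.

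For p = 35% and d = 8%: H = −ln 0.57 = 0.562; hp = 0.562·0.35/0.43 = 0.4575; exp(−0.4575) = 63.3%, against 57.0%.

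Each cell shows Kaplan-Meier with deaths censored / alive and progression-free / gap in points:

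| d | p = 25% | p = 35% | p = 45% |
|---|---|---|---|
| 0% | 75.0 / 75 / 0 | 65.0 / 65 / 0 | 55.0 / 55 / 0 |
| 1% | 74.9 / 74 / 0.9 | 64.8 / 64 / 0.8 | 54.7 / 54 / 0.7 |
| 3% | 74.6 / 72 / 2.6 | 64.4 / 62 / 2.4 | 54.2 / 52 / 2.2 |
| 8% | 73.8 / 67 / 6.8 | 63.3 / 57 / 6.3 | 52.7 / 47 / 5.7 |
| 12% | 73.2 / 63 / 10.2 | 62.3 / 53 / 9.3 | 51.4 / 43 / 8.4 |

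**4. Estimator alone.** A binary PPF that drops deaths from the denominator is (1−p−d)/(1−d). At 35% and 8% this is 0.57/0.92 = 62.0%, against 63.3% by Kaplan-Meier with deaths censored. The difference is 0.4-0.6, 1.0-1.6 and 1.6-2.5 points at 3%, 8% and 12% deaths. The handling of deaths matters more than the choice of estimator.

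**5. Last date of any kind, some 12-month MRIs missed.** Suppose a fraction m of subjects miss the 12-month MRI but have a later date in the database. With deaths censored, the gain is S6·q·m, where S6 = exp(−hp·183/365) and q = 1−exp(−hp·182/365).

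At 35% and 8%: S6 = 0.795 and q = 0.204, so the product is 0.162. For m = 5%, 10% and 20% the gain is 0.8, 1.6 and 3.2 points. Over the grid it is 0.6-1.0, 1.2-2.0 and 2.3-4.0 points.

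**6. Last date of any kind, every MRI done.** I simulated 400,000 subjects at 35% and 8%, with scans uniform within ±14 days of each visit, death as an event, and Kaplan-Meier read at day 365. Censoring at the last scan gives 0.62. Moving event-free subjects to a date after day 365 gives 0.64, about 2 points more. Both exceed the true 0.57, because scans after day 365 fall beyond the cut-off. Assigning in-window scans to the nominal day brings the result within 0.003 of 1−p−d.

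**The case against.** The protocol never says that TTP excludes death, and SAP 5.7.2 states its composite openly with an alternative name. That is true, but the protocol's label reads as progression only, and a reported TTP will be taken that way.

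A reader might infer that the SAP censors deaths in PPF. The documents do not support that. The 5.7.4 list is introduced as what the items will include, so it need not be complete. The TTP list has no separate death date either, only death as a reason for loss, yet TTP counts deaths. What stands is that the handling is unstated and may differ between the two endpoints.

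The SAP does not use the word censored for TTP, EHS or PPF, so last-date censoring is a reading of the item lists with SAP 7.1. The form that supplies the progression date is not identified as a site form. The conflict with the core-laboratory rule rests on the explicit reference to investigator assessment.

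A reader might also infer that the 12-month cut-off is left open, because SAP 5.8 has both a window system and an exact-day system. Section 5.8 introduces these for safety rates, and SAP 5.7.1 gives 365 days as its 12-month example for OS. No fault is claimed there.

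The two PPF estimators can be reconciled by treating Kaplan-Meier as supplementary, which post-hoc may have meant. But that word also covers OS, TTP and EHS, which SAP 5.1 plans by Kaplan-Meier, and nothing says which PPF is primary.

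**Conclusion.** The point holds. On plain text, a composite of progression and death is labelled TTP and rests on the investigators' read against the documents' own core-laboratory rule. PPF has two estimators, and no progression criterion is named. Unstated handling of PPF deaths and follow-up past the last tumour assessment are reasonable readings of the item lists, held with less certainty.

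The sizes depend on assumed rates. If PPF deaths were censored, the overstatement would run from nothing with no deaths to 8.4-10.2 points at 12%. The 81% survival quoted for Child-Pugh B would allow more, but it describes liver disease in general, and the trial admits only A or B7. Last-date censoring adds about 0.6-4.0 points with 5-20% of 12-month MRIs missed. It is not harmless with complete imaging either: about 2 points at a day-365 cut-off with scans spread over ±14 days.

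Nothing here touches the primary alpha, power, N or success rule. The SAP calls these analyses observational. The change should be made, but the trial's conclusion does not depend on it.

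**What to change.** 1. **TTP.** Either define it as progression only, with deaths without progression censored or treated as a competing risk; or keep the composite, call it PFS and record the change to the protocol's endpoint list. State that the loss-to-follow-up dates in SAP 5.7.2 are censoring dates.
2. **PPF.** Define it as alive and without progression at 12 months, with one primary estimator: the protocol's binary proportion with a stated denominator (Kaplan-Meier supportive), or Kaplan-Meier with a recorded change to Protocol 12.1.2. Delete post-hoc for the planned analyses.
3. **Progression.** Base it on core-laboratory reads under one named criterion with its reference scan. Count new intrahepatic lesions, which the mRECIST target-lesion table alone would miss, and site-documented extrahepatic spread. Date progression from the scheduled core-laboratory reads. State how progression seen only on the scan after the second treatment is dated, because Protocol 13.3 lists no core-laboratory read of it. Report investigator-assessed progression as supportive.
4. **Censoring.** Censor TTP, PPF and EHS at the last evaluable tumour assessment, and keep the SAP 7.1 date for OS. Assign in-window 12-month scans (days 351 to 379) to the 12-month time point.

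**Cost.** SAP wording and derivation programming, largely on reads already scheduled, plus whichever protocol changes the chosen options require. PPF may look slightly less favourable, and core-laboratory and site progression dates may differ.
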